2.2 Efficacy Endpoints

The primary endpoint in this study will be a sustained virological response 24 weeks post treatment. The durability of this response will be reassessed 48 weeks after stopping therapy. Secondary endpoints will be changes in HCV RNA levels at 24, 48, and 72 hours, 4 weeks, 24 weeks, and at the end of treatment. Other secondary endpoints will be sustained biochemical responses and improvements of serum alanine aminotransferase levels at 4 weeks, 24 weeks, and at the end of treatment. The definitions of responses are given below.

Sustained virological response: Measured at post treatment week 24, is defined as lack of detectable HCV RNA in serum, by qualitative PCR with a lower limit of sensitivity of 50 IU/ml (e.g., Roche, Amplicor HCV assay).

Durable sustained virological response: Measured 48 weeks following discontinuation of therapy is defined as absence of detectable HCV RNA in serum by qualitative PCR.

Changes in HCV RNA: Measured at 24 hours, 4 weeks, 24 weeks, and at the end of treatment will be assessed by quantitative PCR (Roche, Monitor HCV assay). Changes will be categorized as decreases of <1 log_{10} , 1-2 logs, >2 logs in IU, and negative (<50 IU) by qualitative PCR.

The primary endpoint of the study will be sustained virological response.

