We will also examine adherence as an outcome variable. Mutivariable analyses, using GEE methodology, will be employed to identify factors independently associated with adherence. The primary response variable examined in the analyses will be the dose intake per week for the 48 weeks of the study. Dose intake refers to the weekly doses of ribavirin and peginterferon consumed as recorded by the MEMS cap. Separate regression analyses will be performed to examine the effect of each medication.

We are also interested in examining the relationship between viral kinetics and outcome. Neumann et. al²⁶ and Zeuzem²⁷, discuss the two-phase decline in serum HCV RNA levels following the initiation of therapy consisting of the daily administration of interferon-2b. After an initial 8 to 10 hour pharmacokinetic period, there is an approximate 2.0 log (base 10) decline in serum HCV RNA levels during the next 48 hours by inhibiting viral production. From day 2 on, viral decline is markedly slower, which reflects the clearance of HCV infected liver cells. The viral kinetics following therapy with pegylated interferon and ribavirin may follow a different pattern, possibly reflecting a three-phase, rather than a two-phase, decline. The viral kinetics will be described using nonlinear regression methods to estimate parameters of models of viral infection for each patient. ²⁸ Then, the distributions of these parameters will be compared between racial groups using, for example, the Wilcoxon Rank Sum test. We will use generalized linear models to determine whether the parameters differ by race after adjusting for confounding factors that, ideally, would be specified in advance. Models may be fit for early phase (e.g., days 0-3) to see whether there are race differences in viral production, and for the later time period to see whether there are differences in virion clearance.

For all analyses, a p-value of less than 0.05 will be used to indicate statistical significance.

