Viral Kinetics	X	Х	Х	Х	Х	Х	Х	Х	Х	Х		Х	Х
Pharmaco -kinetics	X	X	x	X	Х	X	Х	Х	Х	Х	X PEG- IFN alfa-2a only		
ALT	Х	Х	Х	Х	Х	Х	Х	Х	Х	Х		Х	Х

 Table 9

 Blood sampling schedule for viral kinetic studies

Blood will be drawn for HCV RNA determination at baseline, days 1, 2, 7, 14, 28 and months 2, 3, 6, 12, 18 and 24 (see Table 9). The frequency of this sampling is to assess the early and late declines with peginterferon alfa-2a and whether there are differences in interferon effectiveness, intrinsic viral clearance, and viral production. Blood for peginterferon alfa-2a serum levels will be obtained at each point where we measure RNA in the first week and selected later time points (see Table 9). 2',5'-OAS, a marker of interferon responsiveness, will also be measured at these time points.

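### The 72-hour HCV RNA endpoint has no blood draw, the example days 0-3 window holds only three samples, and the later-phase parameter is given the wrong mechanism

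*Protocol*

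**What the plan says.** All references are to the protocol.

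- **Endpoint list, Section 2.2:** "Secondary endpoints will be changes in HCV RNA levels at 24, 48, and 72 hours", after which the list adds 4 weeks, 24 weeks and end of treatment.
- **Definition of the same endpoint, Section 2.2:** "Measured at 24 hours, 4 weeks, 24 weeks, and at the end of treatment will be assessed by quantitative PCR". Neither 48 nor 72 hours appears.
- **Schedule, Section 8.1:** "Blood will be drawn for HCV RNA determination at baseline, days 1, 2, 7, 14, 28", followed by monthly time points. Tables 7, 9 and 14 show the same early days, and the Section 4.4 visit list has nothing at day 3.
- **Kinetic analysis, Section 6.0:** the viral kinetics are to be described "using nonlinear regression methods to estimate parameters of models of viral infection for each patient", and the parameters are then compared between the racial groups. On the early window: "Models may be fit for early phase (e.g., days 0-3) to see whether there are race differences in viral production". The same sentence continues "for the later time period to see whether there are differences in virion clearance".
- **Mechanism, Sections 6.0 and 8.1:** Section 6.0 describes an initial period of 8 to 10 hours, then a fall over 48 hours caused by blocked viral production, then a slower decline from day 2 that reflects clearance of infected liver cells. Section 8.1 likewise ties the slower second phase to the death of infected cells.

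**The concern.** A secondary endpoint is named at a time when no blood is taken, so no later analysis document can recover it. The two lists in Section 2.2 also disagree, so an analyst cannot tell which time points make up the endpoint family.

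The same mismatch reaches the kinetic modelling. A window ending at day 3 suggests a day-3 observation that does not exist, and three points limit how rich a per-patient early model can be. If the later-phase slope is reported as virion clearance, a racial difference in it would be credited to a mechanism that the protocol assigns elsewhere. Specific aim 3 compares viral kinetics between the races, so the label affects interpretation.

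**Working it through.** The protocol gives no power or sample-size figure for early kinetics, so there is no stated number to reproduce. The check is a count, followed by an identifiability check.

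**1. Time points set side by side**

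| Time point | Endpoint list (2.2) | Definition (2.2) | Draw scheduled (Tables 7, 9, 14) |
|---|---|---|---|
| 24 hours | yes | yes | yes (day 1) |
| 48 hours | yes | no | yes (day 2) |
| 72 hours | yes | no | **no** |
| 4 weeks | yes | yes | yes (day 28) |
| 24 weeks | yes | yes | yes |
| End of treatment | yes | yes | yes |

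The list names 6 time points, the definition names 4, and the schedule supports 5. At 72 hours, 0 of 400 patients have a scheduled value.

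**2. Samples in the example window**

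Scheduled draws to day 28: {0, 1, 2, 7, 14, 28}. Those within days 0-3: {0, 1, 2}, so n = 3. The screening visit adds a pre-treatment level but no information on the decline.

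For a per-patient fit with p free parameters, the sensitivity matrix is n × p and its rank is at most min(n, p). With n = 3, at most three parameters can be estimated, whatever the model. Residual degrees of freedom are n − p:
- three free parameters: 3 − 3 = 0 (exact fit);
- two-parameter log-linear decline: 3 − 2 = 1.

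**3. Illustration with a standard biphasic model**

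The protocol does not fix a model, so the model and all values here are assumptions: log10 V0 = 6, delay t0 = 9 hours, effectiveness ε = 0.9, virion clearance c = 6/day, infected-cell loss δ = 0.15/day.

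For t > t0: V(t) = V0 [A exp(−λ1(t − t0)) + (1 − A) exp(−λ2(t − t0))], where λ1,2 = ½{c + δ ± √[(c − δ)² + 4(1 − ε)cδ]} and A = (εc − λ2)/(λ1 − λ2).

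| Samples | Free parameters | Rank | Smallest singular value |
|---|---|---|---|
| days 0, 1, 2 | V0, t0, ε, c | 3 of 4 | – |
| days 0, 1, 2 | V0, t0, ε, c, δ | 3 of 5 | – |
| days 0, 1, 2 | V0, ε, c (t0 fixed) | 3 of 3 | 0.037 |
| days 0, 1, 2 | V0, ε, δ (t0, c fixed) | 3 of 3 | 0.227 |
| days 0-3 with a day-3 draw added | V0, t0, ε, c | 4 of 4 | 0.00014 |
| all six draws to day 28 | V0, t0, ε, c, δ | 5 of 5 | 0.00018 |

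A reduced early model can be fitted to the three scheduled points. Adding a day-3 draw would repair the 72-hour endpoint, but under these values a free four-parameter early fit would remain practically unidentified. The fit over 28 days has full rank, with delay and clearance only weakly separated because nothing is drawn between baseline and 24 hours.

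**4. The mechanism label**

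Section 6.0 assigns the decline before day 2 to blocked production and the decline after it to loss of infected cells. Section 8.1 agrees on the second phase. The closing sentence of the same Section 6.0 paragraph assigns the later period to virion clearance. The later-phase label contradicts both descriptions.

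**The case against.** The strongest reply is that these are wording conflicts, and that most of the early-kinetics work survives them. Much of that stands.

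- A reader might infer that the early-kinetics results as a whole cannot be produced. The documents do not support this. The 24- and 48-hour changes have draws, and the generalized estimating equation analysis of HCV RNA changes in Section 6.0 needs no mechanistic fit.
- A reader might infer that three samples face four or more parameters. Section 6.0 fixes neither a model nor a parameter count. Its 8 to 10 hour delay describes daily interferon-2b, and it allows that the pattern may differ here. The days 0-3 fit is optional and given only as an example.
- A reader might infer that the per-patient fits fail in general, and fail more often in one racial group. The main fit is not confined to days 0-3 and is nominally estimable from the draws to day 28. Section 1.1 says that flat responses appear more common among African Americans in small studies, but no failure rate is given or derivable.
- Model details may properly sit in a statistical analysis plan or in the Virology Subcommittee's document (Section 7.4), so their absence is no defect.

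This reply does not rescue the 72-hour endpoint. Section 7.4 does provide for a more closely assessed subset, but Section 2.2 does not restrict the endpoint to one, and no table contains the draw. Nor does it reconcile the two lists in Section 2.2 or the later-phase label.

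**Conclusion.** The point holds in three limited parts.

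1. The 72-hour change in HCV RNA is a named secondary endpoint with no data by design: 1 of 6 listed time points, in all patients. The definition also omits 48 hours, which does have a draw. This rests only on the protocol's own lists and tables.
2. The example days 0-3 window contains three samples, so a per-patient early fit can carry at most three free parameters, with none left to assess fit. That limit is a count and needs no model. The finer results on weak separation depend on the assumed biphasic model and values.
3. The later-period parameter is labelled virion clearance where the protocol's own account makes it infected-cell loss.

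Severity is minor to moderate. The primary endpoint, its sample size and its analysis are unaffected.

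**What to change.** - **Section 2.2:** remove 72 hours. Make the endpoint list and the definition both read 24 hours, 48 hours, 4 weeks, 24 weeks and end of treatment. End of treatment must stay, since both lists already contain it.
- **Section 6.0, early phase:** change the example window from days 0-3 to days 0-2. Use the observed log10 fall at days 1 and 2 as the early-phase measure, or state an early model with no more than three free parameters.
- **Section 6.0, later phase:** relabel the parameter as infected-cell loss. Section 8.1 lists intrinsic viral clearance among the quantities of interest, so say which fit would supply it if that comparison is kept.

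A nonlinear mixed-effects model over all patients is one option, not a required correction. If it shared or fixed clearance across patients, it would remove the clearance comparison that Section 8.1 names.

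The cost is a wording change in two sections, with no extra visit or blood. Adding a day-3 draw instead would rescue the 72-hour endpoint at the price of another visit, and would not by itself support a richer early model.

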3.5 Premature Discontinuation

Treatment may be discontinued prematurely for the following reasons:

- 1. Participant requests termination of the study medication;
- 2. Participant is intolerant of the study medication despite predetermined dose reductions and side effect management strategies;
- 3. Safety concerns at the discretion of the investigator. These concerns will be documented in the source documents.

Participants who discontinue treatment prematurely for the above reasons will be encouraged to remain in the post-treatment follow-up period for an additional 24 weeks, unless they withdraw consent. For those discontinued prematurely, blood samples will be obtained as listed for the week 48 end-of-treatment visit.

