4.3 Baseline Visit (Day 0): Once the patient has completed the two screening visits and has been confirmed to be eligible, he/she will return for additional laboratory studies and comprehensive instruction in self-injection techniques by study personnel. These three visits, screening 1, screening 2, and baseline (day 0) will occur within 56 days.

Interim Medical History	
CBC/Differential	
Chemistry	ALT, AST, AlkPO4, total and direct bilirubin, fasting triglycerides, glucose, insulin
Serum Storage	Serum 3ml
Viral Genetics	
Patient Genetics	
Viral Kinetics	HCV RNA quantitative
Pharmacokinetics	Peginterferon alfa-2a levels, 2',5'-OAS serum activity
Interferon Signaling	
Pregnancy Test	Urine
Adherence MATI	
Medication Education	Self-injection techniques (including video), use of MEMS caps, adherence materials
Study Medication Administration	Supervised by research coordinator

Table 6 Baseline (Day 0) visit

4.4 Treatment Period: Pegylated interferon will be administered as a weekly subcutaneous injection and ribavirin will be administered as tablets twice daily. Treatment will be continued for 48 weeks (except in the absence of virological response as defined below). During the treatment period, participants will return for safety and efficacy evaluations at weeks 1, 2, 4, 6 (safety labs only), and 8, and then monthly until treatment is completed.

Efficacy assessment at week 24 will determine if participants are eligible to continue the full 48 weeks of treatment. Participants who have a positive qualitative test result, in duplicate, will be discontinued from study medication at week 24. These participants will then enter the follow-up period and be followed for an additional 24 weeks (post-treatment weeks 4, 12, 24). If they begin other antiviral therapy, they will be discontinued from follow-up.

Interim Medical History	
Symptom-directed Physical Exam	Vital signs and weight at each visit; physical exam every 3 months or as needed
Adverse Event Assessment	
Concurrent Medication Assessment	
CBC/Differential	Each visit (except days 1 and 2)
Chemistry	Each visit except week 1; ALT, AST, AlkPO4, total and direct bilirubin, albumin, uric acid, BUN, creatinine, glucose. Fasting triglycerides, glucose, and insulin at week 24, and week 48 for responders only.
Pregnancy Test	Urine, each visit (except days 1and 2)
TSH	Weeks 12, 24, 36, 48
PT/PTT	Weeks 24 and 48

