The proportion of African Americans and Caucasians with SVR will be compared using the chi-square test of association. The association between race and SVR after adjusting for potential confounders such as adherence, HCV sub-genotype, initial viral level, ALT, body mass index, and baseline histology will be assessed through multiple logistic regression analyses. The Hosmer-Lemeshow statistic will be calculated to determine if there is evidence that the final multiple logistic regression model does not fit. ²³ These

analyses will be repeated for durable viral response, i.e., having undetectable viral RNA 12 months following treatment discontinuation.

Generalized estimating equation (GEE) methods of Zeger and Liang.^{24,25} will be used to assess the differences between the racial groups with respect to changes in serum HCV RNA levels during therapy. This approach models both the regression of the response variable on the independent variables and accounts for the correlated nature of the responses. Analyses using conventional regression methods could provide erroneous variance estimates and loss of statistical efficiency because of the conventional assumption that each response is statistically independent. As a result, invalid inferences could be made if the conventional approach were applied to these longitudinal data.

The models examining response to treatment will include measures of adherence. As an initial step in examining adherence, graphical displays of the dosing history of each participant will be plotted and compared to the prescribed dosing regimen. Graphs include chronological plots showing the date and time of dose intake and frequency histograms of inter-dose intervals. The inter-dose interval representing the length of time between two successive doses will be calculated. For ribavirin, the optimal inter-dose interval is 12 hours and for peginterferon it is 7 days. Longer dosing intervals represent non-adherence and times in which the participant theoretically did not have adequate inhibitory drug concentration. In addition, summary statistics of adherence such as the percentage of prescribed doses taken and the percentage of drug holidays will be derived from the MEMS cap data. GEEs with multiple responses and adherence as a time-dependent covariate will be examined.

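### Durable SVR does not require SVR at week 24, and the rule on other antiviral therapy misses patients who relapse, so a response to another treatment can count as durable

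*Protocol*

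**What the plan says.** **Endpoints.** Section 2.2 fixes each endpoint by a test at one time. For SVR, the primary endpoint: "Measured at post treatment week 24, is defined as lack of detectable HCV RNA in serum, by qualitative PCR". For durable SVR: "Measured 48 weeks following discontinuation of therapy is defined as absence of detectable HCV RNA in serum by qualitative PCR". Section 6.0 carries the second into the analysis as "having undetectable viral RNA 12 months following treatment discontinuation". None of these lines mentions the week-24 result as a condition for durability, or treatment received after the study regimen.

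**Purpose.** Section 2.2 introduces the later assessment thus: "The durability of this response will be reassessed 48 weeks after stopping therapy". Section 3.1 likewise says that the durability of SVR is what is measured at 48 weeks.

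**Other therapy.** Section 4.4 contains the only rule. It opens with "Participants who have a positive qualitative test result, in duplicate, will be discontinued from study medication at week 24", places these participants in a 24-week follow-up, and adds: "If they begin other antiviral therapy, they will be discontinued from follow-up". Section 6.0 counts participants without outcome data as treatment failures.

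**Everyone else.** Week-24 responders are treated to week 48 and then seen at post-treatment weeks 4, 12, 24, 36 and 48 (Section 4.5). Those who stop early "will be encouraged to remain in the post-treatment follow-up period for an additional 24 weeks" (Section 3.5). Neither section says what happens to the endpoint if other antiviral therapy is started.

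**The concern.** A durability endpoint should be nested in the response whose durability it measures. As defined, it is not: a patient can fail SVR at week 24 and still be a durable SVR at week 48. The most direct route is retreatment after relapse. The Protocol foresees other antiviral therapy but regulates it only in patients who are already non-responders, where it can hardly change the result. In patients who respond and then relapse, it can turn a failure into a success.

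At stake is whether the endpoint describes the study regimen or the regimen plus whatever followed. The study compares two racial groups, so the error matters for the comparison if it falls unequally on them.

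**Working it through.** **1. Which participants the stated rules cover**

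| Participant | Planned follow-up | Rule on other therapy | Status if negative on other therapy at the test |
|---|---|---|---|
| Positive in duplicate at treatment week 24 | 24 weeks (4.4, 4.5) | Leaves follow-up (4.4); failure if no outcome data (6.0) | Failure |
| Week-24 responder who relapses | 48 weeks (4.5) | None | Durable SVR at week 48; SVR if all happens before week 24 |
| Early stopper | 24 weeks, encouraged (3.5) | None | SVR possible; no scheduled week-48 sample, so failure for durable SVR (6.0) |

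**2. One patient traced through.** Undetectable at treatment week 24, treated to week 48, detectable at post-treatment week 24: not an SVR. Starts other anti-HCV therapy, undetectable at post-treatment week 48: meets the durable definitions in Sections 2.2 and 6.0. The patient is a durable SVR without ever having been an SVR.

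**3. The two windows.** For durable SVR, relapse, start of other therapy and clearance have up to 48 weeks. For SVR they must all fall within 24 weeks. The first follow-up visit is at week 4, so at most 24 − 4 = 20 weeks remain after the earliest scheduled detection.

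**4. The plan's own figure.** Section 6.0 gives 80% power for 40% against 26%, with 200 per group and two-sided alpha 0.05. With

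power = Φ{[|p1 − p2| − 1.96·√(2p̄(1 − p̄)/n)] / √([p1(1 − p1) + p2(1 − p2)]/n)}, p̄ = (p1 + p2)/2,

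the values p1 = 0.40, p2 = 0.26, p̄ = 0.33, n = 200 give (0.14 − 0.0922)/0.0465 = 1.03, so power is 84.8%. With a continuity correction it is 82.2%. The rate detectable at exactly 80% power is 26.8% uncorrected and 26.35% corrected; the latter rounds to the stated 26%. The design figure is reproduced.

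**5. Effect of false responders.** The Protocol gives no relapse or retreatment rates, so the counts below are assumptions. Each false responder adds 1/200 = 0.5 points to a cohort's rate. The table uses the SVR design rates because none are given for durable SVR. Power is uncorrected.

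| False responders, White/Caucasian | False responders, Black/African American | Observed rates | Difference (points) | Power |
|---|---|---|---|---|
| 0 | 0 | 40% v 26% | 14 | 84.8% |
| 2 | 2 | 41% v 27% | 14 | 84.3% |
| 4 | 4 | 42% v 28% | 14 | 83.8% |
| 6 | 6 | 43% v 29% | 14 | 83.3% |
| 0 | 4 | 40% v 28% | 12 | 71.8% |
| 0 | 6 | 40% v 29% | 11 | 63.9% |
| 4 | 0 | 42% v 26% | 16 | 92.5% |
| 6 | 0 | 43% v 26% | 17 | 95.0% |

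The last two rows are not a gain: they give the chance of significance for an inflated difference.

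**The case against.** **The intent is stated.** The endpoint's name, the introductory sentence in Section 2.2 and Section 3.1 all point to SVR first. This stands as to the concept. It does not repair the definition line or the analysis text, and those are what would be applied to the data.

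**There is a retreatment rule.** A reader might infer that the plan says nothing about other therapy. That is not so: Section 4.4, read with the missing-data rule in Section 6.0, makes failures of week-24 non-responders who leave follow-up for other therapy. The gap is in whom the rule reaches.

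**The primary endpoint is little exposed.** A reader might infer that SVR is as vulnerable as durable SVR. The documents do not support this. The window is short, and Sections 1.1 and 1.2 present interferon with ribavirin as the most effective therapy and genotype 1 as the hardest to treat. No alternative is named that would clear relapsers quickly. The reasons for early stopping in Section 3.5 are request, intolerance and safety, and nothing there suggests prompt retreatment.

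**The size is assumed.** This stands in full. The Protocol has no data on retreatment by race, so unequal misclassification is a possibility and not a finding.

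**An analysis plan may settle it.** It may, and handling details belong there. But the Protocol itself fixes a definition in two places that departs from the purpose it states.

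**Conclusion.** The point holds, chiefly for durable SVR. Its definition omits SVR at week 24 and so conflicts with its stated purpose, and the rule on other therapy leaves out relapsing responders, the group in whom it would change the durable result. For SVR the same route exists, including in early stoppers, but it is less likely.

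No figure in the Protocol is wrong because of this. Equal misclassification leaves the difference at 14 points and costs at most 84.8 − 83.3 = 1.5 points of power for up to six patients per cohort. Four to six false responders in one cohort only would shift the difference by 2 to 3 points, towards or away from zero. Those counts, and their falling in one cohort, are assumptions; a reader should not take them as evidence that the racial comparison is biased.

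A reader might also infer that any detectable result after treatment should disqualify a patient, even without other therapy. The documents do not support that: it would change the primary endpoint as stated, and duplicate testing is specified only at treatment week 24, with no confirmatory test scheduled afterwards.

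**What to change.** In Sections 2.2 and 6.0:

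1. Define durable SVR as SVR at post-treatment week 24 and undetectable HCV RNA at post-treatment week 48.
2. For both endpoints and all participants, count anyone who starts non-study anti-HCV therapy before the assessment as a non-responder for that endpoint and later ones. This gives relapsers and early stoppers the status that Sections 4.4 and 6.0 already lead to for week-24 non-responders who leave follow-up. A participant who is an SVR at week 24 and starts such therapy afterwards keeps SVR and fails durable SVR.

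The cost is wording. Table 8 already lists concurrent medication in follow-up; the start date of any anti-HCV therapy should be taken from that record. Table 9 lists fewer post-treatment HCV RNA samples than Tables 8 and 14, but all three include the two that are needed (post-treatment weeks 24 and 48, shown as weeks 72 and 96 in Table 9). One consequence should be accepted knowingly: a participant without a week-24 result, already a failure for SVR under Section 6.0, would also fail durable SVR in the primary analysis.

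The change concerns endpoint classification only. It says nothing about who may receive other therapy or when.
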